- 3) lack of any data about the patient after administration of the study drug.

This sample, the most consistent with the “Intention-to-treat” principle, will be used for the ***Intention-to-treat analysis (ITT analysis)*** of the study therapy efficacy.

⁷ Licensee: OOO "NPF "Materia Medica Holding", No. 70100045

Per protocol set. This sample includes all patients who have received the complex therapy under the Protocol and completed all the scheduled visits. This sample will be used for the ***Per Protocol analysis (PP- analysis)*** of the study therapy efficacy. The list of deviations that may result in complete or partial invalidity of data is developed by a medical expert jointly with a biostatistician according to the study design:

1. The protocol deviations potentially resulting in partial or complete invalidation of the study patient's data: Violation of visit schedule.
2. Inappropriate distribution/supply of the study drug.
3. Prescription of prohibited therapy.
4. $\geq 25\%$ increase or reduction in the amount of the study therapy administered.
5. Inability to assess the patient's compliance using the formula (e.g. loss of pack with the product).
6. Major discrepancies between source documents and CRF detected during monitoring or another authorized check.
7. Violation of the procedure of obtaining informed consent.
8. Non-compliance with the clinical study protocol procedures.
9. Inability to collect all the patient's data used for evaluation of the study endpoints ⁸(e.g. lack of entries in source documents required for verification of inclusion/exclusion criteria, safety and efficacy criteria).
10. Any other protocol deviations covered by the term “major deviation”.

Evaluation of sample size

The sample size was assessed on the basis of the following rules and assumptions:

1. Statistical provisions.
 - 1.1 the power of the statistical tests “ $P = (1 - \beta)$ ” is assumed to be 80% (the probability of correct rejection of the null hypothesis is 0.8);
 - 1.2 the probability of a type I error “ α ” is allowed to be less than 5% (the probability of the erroneous acceptance of an alternative hypothesis is less than 0.05);
 - 1.3 the statistical criteria used are 2-sided;
 - 1.4 the protocol contains evaluation of minimum detectable effect at fixed: sample size, population variance, type 1 and 2 error values;
 - 1.5 the ratio between the sample sizes of the study drug and placebo groups is 1:1 (1 study drug patient - 1 placebo patient);

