Note. Red area is empirical distribution of time to resolution of symptoms in Product group (number of simulation repetitions $N=10^5$). Red curve is approximate parametric distribution for the groups.

Therefore, given fixed sample ($N_{pp}=120$) obtained above for population standard deviation ($sd=1.38$) and levels of errors ($\alpha=0.05$, $\beta=0.2$), the minimum detectable effect in the study will be **0.71 day**. When planning the study withdrawal rate of 50% patients was taken¹² ($C_w=0.5$). In total 240 patients will participate in the study.

Statistical criteria

All the statistical calculations will be performed using two groups of statistical criteria:

- parametric – to obtain effective evaluations for parameters of random values, if the relevant conditions of applicability of methods/models are not violated (e.g. sphericity, normality, proportionality of risks, etc.);
- non-parametric – in any other cases.

Parametric criteria

⁹ Based on the clinical trial “A study to assess the therapeutic efficacy and safety of Anaferon against influenza and other upper respiratory tract infections in adults” [11]. Duration distributions for symptom domains are considered independent. 95% confidence interval is taken for the corresponding standard deviations.

¹⁰ The data resulting in major variance evaluation are used.

¹¹ On the distribution of the maximum of N independent normal random variables: IID and INID cases. SDSSU Multidisciplinary Research Journal Vol. 1 No. 2±2013

¹² This rate is complex: 10% patients will be screening failures or will withdraw for other reasons specified in the relevant protocol section, 44% remaining patient will not have the diagnosis verified by PCR.

The application of parametric criteria will be accompanied by a check of models for applicability (e.g. Kolmogorov-Smirnov test, Shapiro-Wilk test, etc.).

The following parameters and approaches are to be used:

1. To evaluate the differences of continuous variables obtained in one group at two different visits – Student's test for matched samples.
2. To evaluate the temporal dynamics of the compared indicators – analysis of variance (ANOVA) or covariance (ANCOVA) in the modification with repeated measures.
3. In case of multiple comparisons between the groups will apply a variety of corrections for multiplicity (Dunnett, Tukey, Scheffe, Holm adaptive test), etc.

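### Does treating the two symptom-domain durations as independent make the 0.71-day detectable effect at 80% power too optimistic?

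*Combined protocol and SAP*

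**What the plan says.** Under the heading Evaluation of sample size, items 1.1 to 1.5 fix the error rates and allocation: power "is assumed to be 80% (the probability of correct rejection of the null hypothesis is 0.8"), type I error such that "the probability of the erroneous acceptance of an alternative hypothesis is less than 0.05", "the statistical criteria used are 2-sided", and "the ratio between the sample sizes of the study drug and placebo groups is 1:1". The number of patients is fixed and the detectable difference is solved for (item 1.4), using a two-sample normal formula for a difference in means (item 1.6).

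Item 2 supplies the SD. Time to resolution is the maximum of N(2.6, 1.77) and N(5, 1.47), approximated by a normal with mean 5.17 and SD 1.38. Footnote 9 adds "Duration distributions for symptom domains are considered independent" and goes on to say that a 95% confidence interval was used for the domain SDs, without naming the limit. Footnote 10 adds "The data resulting in major variance evaluation are used". With 120 per-protocol patients, "the minimum detectable effect in the study will be" 0.71 day. A withdrawal coefficient of 0.5 takes this to 240 enrolled. The Interim analysis section allows an optional blinded look to refine population parameters, with an increase in sample size only.

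**The concern.** A patient whose infection runs long in one symptom domain will probably run long in the other. Independence is therefore a doubtful model for two durations in the same person, and the plan gives neither a reason for it nor a sensitivity range. It is also the favourable choice: among correlations of zero or more, independence gives the smallest SD for the longer of the two durations. That sits awkwardly beside footnote 10, which shows an intention to plan on the larger variance.

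Because the sample is fixed, 0.71 day at 80% power is the only statement the protocol makes about what the trial can detect. If the true SD were larger, a non-significant result would be read against a sensitivity the trial did not have. Two further points seem to push the same way. The formula is a z-test on complete times, although survival procedures are among the listed tools. And the modelled event appears stricter than the endpoint in footnote 1, which tolerates some residual symptoms.

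**Working it through.** **Inputs.** Two-sided alpha 0.05, power 0.80 and 1:1 allocation (items 1.1 to 1.5); domain durations N(2.6, 1.77) and N(5, 1.47) and planning SD 1.38 (item 2); 120 per-protocol patients in all, from 240 × (1 − 0.5), so 60 per arm.

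**Reproducing the plan's figure.** Detectable effect = (1.960 + 0.842) × SD × √(2/60). With SD 1.38 this is 2.802 × 1.38 × 0.1826 = 0.706. A t-test version gives 0.712. Both agree with 0.71. Reading 120 as the number per arm gives 0.50, so 60 per arm is what the plan used. Power at exactly 0.71 day is Φ(0.71/0.252 − 1.960) = Φ(0.858) = 80.5%.

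**SD of the longer duration at correlation ρ.** Let a = √(1.77² + 1.47² − 2ρ × 1.77 × 1.47) and α = (2.6 − 5)/a, with Φ and φ the standard normal distribution function and density. Then

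- E(max) = 2.6Φ(α) + 5Φ(−α) + aφ(α)
- E(max²) = (2.6² + 1.77²)Φ(α) + (5² + 1.47²)Φ(−α) + (2.6 + 5)aφ(α)

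and the SD is √[E(max²) − E(max)²]. At ρ = 0, a = 2.301 and α = −1.043, so the mean is 5.18 and the SD 1.360, close to the plan's 5.17 and 1.38. A simulation with a million draws agrees.

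| ρ | SD | Detectable effect at 80% (days) | Power at 0.71 day |
|---|---|---|---|
| −0.5 | 1.23 | 0.63 | 88.4% |
| 0 | 1.36 | 0.70 | 81.6% |
| 0.1 | 1.38 | 0.71 | 80.3% |
| 0.2 | 1.40 | 0.72 | 79.2% |
| 0.3 | 1.42 | 0.73 | 78.2% |
| 0.4 | 1.44 | 0.73 | 77.3% |
| 0.5 | 1.45 | 0.74 | 76.5% |
| 0.7 and above | 1.47 | 0.75 | 75.3 to 75.5% |

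The SD levels off near 1.47 because, at high correlation, the maximum is almost always the second domain, whose own SD is 1.47. Power is nearer 75% than 80% only for ρ above about 0.4. The plan's SD of 1.38 is the exact value for ρ of about 0.1. Independence is the lowest-variance case only if negative correlations are excluded.

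**What the confidence interval in footnote 9 could do.** At most, correlation multiplies the planning SD by 1.47/1.38 = 1.065. Suppose the domain SDs are upper limits of two-sided 95% intervals (an assumption). For a source group of size n, the upper limit exceeds the point estimate by the factor √[(n − 1)/χ²(0.025; n − 1)]. The source size is not given, so these values are illustrative:

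- n = 60: factor 1.22
- n = 200: factor 1.11
- n = 500: factor 1.066

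At n = 500 the point estimate behind 1.47 would be 1.47/1.066 = 1.38. For source groups up to about 500, the SD based on point estimates would then be no larger than the planning value even at ρ near 1, and 80% power at 0.71 day would hold.

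**The case for a change.** The strongest case for a change is that an unsupported and favourable assumption is presented as a single figure, when a few sentences would give a range. The confidence-interval offset is itself uncertain, since footnote 9 does not name the limit. The blinded interim look could correct the SD but is optional. Log-rank simulations on the same durations gave power at 0.71 day of about 73 to 75% under independence and about 70% at ρ = 0.5, with 80% reached near 0.77 and 0.8 day.

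Some of this stands. Independence is not justified in the text, positive correlation is plausible, and a range would tell the reader more than a point.

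The rest carries less weight. Footnote 10 concerns which source data were chosen and says nothing about dependence between domains, so no stated rule is broken. The log-rank results depend on a test the plan does not name for the primary endpoint: item 1.6 states the hypotheses on means, and Statistical criteria lists t-test and Mann-Whitney procedures alongside survival ones. They also assume a pure shift in time. Which test is primary is a separate question. The gap between the modelled event and footnote 1 comes with no direction or size for the SD, so it cannot support a claim about power.

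**Conclusion.** No change follows. The 0.71-day figure is correct arithmetic on disclosed inputs. Allowing for positive correlation raises the detectable effect from 0.71 to at most 0.75 day, about one hour, and lowers z-test power at 0.71 day to between 80% and 75% for ρ from about 0.1 to 1. The 75% end needs ρ of about 0.7 or more, and the documents supply no value. If the domain SDs are upper confidence limits, the loss may already be covered, so the documents do not show that the design misses 80% power.

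Replacing 1.38 with 1.47 would put a worst-case correlation on top of SDs that may already be inflated, which the sponsor's statistician could fairly dispute. Holding 0.71 day at SD 1.47 would take 68 per arm per protocol, or 2 × 68/0.5 = 272 enrolled instead of 240. That is not warranted on an unknown correlation, particularly when the plan already permits a blinded look at the SD with an upward adjustment. Without that increase, restating the figure would leave sample size, conduct and analysis untouched. These conclusions assume 60 evaluable patients per arm, the plan's normal model for each domain and a comparison of means.
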